**Figure 2: Procedures for Screening Vital Signs (Blood Pressure – Pulse) – Healthy Subjects Only**

DBP=diastolic blood pressure; eCRF=electronic case report form; SBP=systolic blood pressure

### 7.2.2.5 Clinical Laboratory Evaluations

All clinical laboratory assays will be performed according to the laboratory’s normal procedures. Reference ranges are to be supplied by the laboratory and will be used to assess the clinical laboratory data for clinical significance and out-of-range pathological changes. The investigator should assess out-of-range clinical laboratory values for clinical significance, indicating if the value(s) is/are not clinically significant or clinically significant. Abnormal clinical laboratory values, which are unexpected or not explained by the subject’s clinical condition, may, at the discretion of the investigator or sponsor, be repeated as soon as possible until confirmed, explained, or resolved.

The following clinical laboratory assessments will be performed:

### Biochemistry

Blood samples (8.5 mL) for serum biochemistry will be collected into a gel separator tube at the time points described in [Table 1](#), [Table 2](#), and [Table 3](#). The following parameters will be assessed:

Sodium	Phosphorus	$\beta$ -hCG a
Potassium	Total protein	
Glucose	Total CO 2 (Bicarbonate)	
Blood urea nitrogen	Albumin	
Creatinine	Aspartate transaminase	
Calcium	Alanine transaminase	
Chloride	Gamma glutamyl transferase	
Thyroid stimulating hormone (TSH)	Alkaline phosphatase	
Thyroxine (T4 total)	Total bilirubin	
Triiodothyronine (T3)	Uric acid	

a $\beta$ -hCG=beta-human chorionic gonadotropin. Females only.

### Hematology

Blood samples (4 mL) for hematology will be collected into a ethylenediaminetetraacetic acid tube at the time points described in [Table 1](#), [Table 2](#), and [Table 3](#). The following parameters will be assessed:

Hemoglobin	Total neutrophils (absolute)
Hematocrit	Eosinophils (absolute)
Red blood cells	Monocytes (absolute)
Platelet count	Basophils (absolute)
White blood cell count; total and differential	Lymphocytes (absolute)

## Urinalysis

A urine sample for urinalysis will be collected at the time points described in [Table 1](#), [Table 2](#), and [Table 3](#). The following parameters will be assessed:

pH	Blood	Nitrites
Glucose	Ketones	Leukocyte esterase
Protein	Bilirubin	Specific gravity

Microscopic examination will be conducted if protein and/or blood is/are detected during urinalysis. At a minimum the microscopic examination will consist of red blood cells, white blood cells, casts, and bacteria.

### 7.2.2.6 Pregnancy Test

For all female subjects (regardless of reproductive potential status), a serum pregnancy test will be performed at the visits specified in [Table 1](#); or if pregnancy is suspected; or on withdrawal of the subject from the study.

### 7.2.2.7 Drug and Alcohol Screen

A urine screen for drugs of abuse and alcohol will be performed at the time points described in [Table 1](#). Additional drug and alcohol screens may be performed at the investigator's discretion.

Urine samples are to be tested for amphetamines, barbiturates, benzodiazepines, cannabinoids, cocaine, methadone, opiate metabolite, and phencyclidine.

Results of urine drug and alcohol screens will be reviewed and verified by the study monitor, but will not be collected in the CRF database.

Any positive result for drugs of abuse or alcohol at screening or on Day -1 will exclude the subject from further participation in the study.

### 7.2.2.8 Serology Screen

At the screening visit, a blood sample of approximately 8.5 mL will be drawn into a serum separator tube to test for the presence of HIV, hepatitis B surface antigen (HBsAg), and hepatitis C virus (HCV) antibody.

The test results must be confirmed negative prior to enrollment in the study. If a test result is positive, the subject will be excluded from entering the study. Results of the virology screen will be reviewed and verified by the study monitor, but will not be collected in the CRF database.

### 7.2.2.9 Electrocardiogram

Twelve-lead ECGs will be performed at the times specified in [Table 1](#), [Table 2](#), and [Table 3](#) using the standard methods/equipment at the CRC.

The following parameters will be recorded on the appropriate CRF page: heart rate, PR, RR, QRS, and QT intervals. The QTcB and QTcF will be derived from the data in the database. The investigator's assessment of the ECG tracing as normal or abnormal must be documented, and if abnormal, his/her determination of whether the abnormality is clinically significant or not will be documented on the tracing and recorded in the CRF.

The subject should be asked to remove all clothing that covers the location of lead placement. The subject must be resting in the supine position for at least 5 minutes prior to collecting the ECG.

In some cases, it may be appropriate to repeat abnormal ECGs to rule out improper lead placement as contributing to the ECG abnormality. It is important that leads are placed in the same positions each time in order to achieve precise ECG recordings.

One complete recording, including a 10-second rhythm strip, should be taken at each time point. It should be immediately assessed as a valid recording and if not valid, it should be repeated. Invalid recordings will not be entered in the CRF. The ECG collected predose on Day 1 will serve as the subject's baseline ECG.

### **7.2.3 Pharmacokinetic Procedures**

The name and address of the bioanalytical laboratory(ies) for this study will be maintained in the investigator's files at the/each site and in the Trial Master File at the sponsor.

Actual pharmacokinetic blood sample collection times versus time of dosing will be monitored. The sponsor's expectation is that the investigator will ensure that every effort is made to collect all pharmacokinetic blood samples at the precise protocol scheduled time. Pharmacokinetic blood collection must not deviate from the nominal collection time set forth in the protocol by more than  $\pm 5$  minutes from samples drawn within 4 hours post dose or by more than  $\pm 15$  minutes for samples drawn beyond 4 hours post dose. Samples drawn outside these parameters will be considered a protocol deviation.

#### **7.2.3.1 Blood Sample Collection and Handling Procedures**

Blood samples will be collected at the time specified in [Table 1](#), [Table 2](#), and [Table 3](#) to measure plasma concentrations of anagrelide, its active metabolite, BCH24426 (3-hydroxy-anagrelide), RL603, and omeprazole. Other potential metabolites may also be determined as appropriate.

A full description of the PK blood collection, handling, storage, and shipping can be found in the laboratory manual.

Plasma sample tubes for bioanalysis must be freezer-safe and identified with freezer-safe labels provided by the CRC. The labels will contain the following information:

- Study number (SPD422-113)
- Subject identifier
- Analyte (anagrelide or omeprazole)
- Nominal day (Day 1, Day 6...)
- Nominal time
- Matrix identifier (plasma)
- Split (primary or backup or aliquot 1 or aliquot 2)

### **7.2.3.2 Shipment of Pharmacokinetic Samples**

All pharmacokinetic samples should be placed in a cryo-box, double-bagged to contain leaks and packed with a sufficient quantity of dry ice to ensure that they remain frozen for at least 72 hours to allow for delays in shipment. All applicable shipping regulations must be followed. Shipments should be scheduled so that no samples arrive on the weekend and should be shipped Monday-Wednesday only. Samples should be transported to ensure that they arrive at the bioanalytical laboratory between the hours of 9:00 AM and 4:00 PM. The recipient and primary Shire contact must be notified by telephone or e-mail when the samples are shipped and they must be provided with the shipment tracking number.

Full directions for shipment of all PK samples, (along with the corresponding documentation) can be found in the laboratory manual provided under separate cover.

Pharmacokinetic samples will be stored nominally at -80°C for anagrelide and -20°C for omeprazole at YBS prior to and after analysis until their disposal is authorized by Shire.

### **7.2.3.3 Plasma Drug Assay Methodology**

Plasma sample analysis will be performed according to the relevant Standard Operating Procedures at the contract bioanalytical lab.

Plasma concentrations will be measured using the most current validated bioanalytical methods. In addition, selected plasma samples may be used to investigate incurred sample reproducibility (full details will be described in the bioanalytical study plan). The presence of other metabolites or artifacts may be monitored or quantified as appropriate. Raw data will be stored in the archive of the designated bioanalytical contract laboratory.

**Table 4: Volume of Blood to Be Drawn from Each Subject**

Assessment		Sample Volume (mL)	Number of Samples	Total Volume (mL)
Anagrelide Pharmacokinetic samples a		6 a	20	120
Omeprazole Pharmacokinetic samples		2	13	26
HBsAg, HIV, HCV		8.5	1	8.5
Safety	Biochemistry and $\beta$ -hCG b	8.5	5	42.5
	Hematology	4	5	20
Thyroid function		5	1	5
Total mL				222

$\beta$ -hCG=beta-human chorionic gonadotropin; HBsAg=hepatitis B surface antigen; HCV=hepatitis C virus; HIV=human immunodeficiency virus

a If a catheter is used, the first mL is to be discarded; then take 4 mL into appropriate tube for pharmacokinetic sample. A total of 5 mL of blood drawn has been used in determination of sample volume.

b  $\beta$ -hCG testing for females only.

During this study, it is expected that approximately 222 mLs of blood will be drawn from all subjects, regardless of sex.

Note: The amount of blood to be drawn for each assessment is an estimate. The amount of blood to be drawn may vary according to the instructions provided by the manufacturer or laboratory for an individual assessment; however, the total volume drawn over the course of the study should be approximately 222 mLs. When more than 1 blood assessment is to be done at the time point/period, if they require the same type of tube, the assessments may be combined.

## 8. ADVERSE AND SERIOUS ADVERSE EVENTS ASSESSMENT

### 8.1 Definition of Adverse Events, Period of Observation, Recording of Adverse Events

An AE is any untoward medical occurrence in a clinical investigation subject administered a pharmaceutical product and that does not necessarily have a causal relationship with this treatment. An AE can therefore be any unfavorable and unintended sign (including an abnormal laboratory finding), symptom, or disease temporally associated with the use of a medicinal (investigational) product, whether or not related to the medicinal (investigational) product (International Conference on Harmonisation [ICH] Guidance E2A 1995).

All AEs are collected from the time the informed consent is signed until the defined follow-up period stated in Section 7.1.3. This includes events occurring during the screening phase of the study, regardless of whether or not investigational product is administered. Where possible, a diagnosis rather than a list of symptoms should be recorded. If a diagnosis has not been made, then each symptom should be listed individually. All AEs should be captured on the appropriate AE pages in the CRF and in source documents. In addition to untoward AEs, unexpected benefits outside the investigational product indication should also be captured on the AE CRF.

All AEs must be followed to closure (the subject's health has returned to his/her baseline status or all variables have returned to normal), regardless of whether the subject is still participating in the study. Closure indicates that an outcome is reached, stabilization achieved (the investigator does not expect any further improvement or worsening of the event), or the event is otherwise explained. When appropriate, medical tests and examinations are performed so that resolution of event(s) can be documented.

#### 8.1.1 Severity Categorization

The severity of AEs must be recorded during the course of the event including the start and stop dates for each change in severity. An event that changes in severity should be captured as a new event. Worsening of pre-treatment events, after initiation of investigational product, must be recorded as new AEs (for example, if a subject experiences mild intermittent dyspepsia prior to dosing of investigational product, but the dyspepsia becomes severe and more frequent after first dose of investigational product has been administered, a new AE of severe dyspepsia [with the appropriate date of onset] is recorded on the appropriate CRF).

The medical assessment of severity is determined by using the following definitions:

- Mild:** A type of AE that is usually transient and may require only minimal treatment or therapeutic intervention. The event does not generally interfere with usual activities of daily living.
- Moderate:** A type of AE that is usually alleviated with specific therapeutic intervention. The event interferes with usual activities of daily living, causing discomfort but poses no significant or permanent risk of harm to the research subject.
- Severe:** A type of AE that interrupts usual activities of daily living, or significantly affects clinical status, or may require intensive therapeutic intervention.

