**Secondary endpoint:**

Safety will be assessed for the following evaluations for anagrelide alone, omeprazole alone, and anagrelide and omeprazole combination treatments:

Number, severity, seriousness, and causality of treatment emergent adverse events (TEAEs)

Changes in physical examination, vital signs, electrocardiogram (ECGs), and clinical laboratory results (hematology, chemistry, and urinalysis) from baseline to post-baseline time points.

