## 9.9 Safety Analyses

The safety endpoints will be summarized with descriptive statistics for the safety set.

Relevant safety endpoints as well as their changes from baseline will be summarized. Baseline is defined as the last assessment prior to the first dose of investigational product. Potentially clinically important findings will also be summarized or listed. The potentially clinically important values will be defined in the SAP.

Adverse events will be coded using the Medical Dictionary for Regulatory Activities. The number of events, incidence, and percentage of treatment-emergent adverse events will be calculated overall, by system organ class, by preferred term, and by treatment group. Treatment-emergent adverse events will be further summarized by severity and relationship to investigational product. Adverse events related to investigational product, AEs leading to withdrawal, SAEs, and deaths will be similarly summarized/listed.

Safety will be assessed by treatment emergent adverse events (TEAEs), new findings from physical examination, evaluation of blood pressure, heart rate, new findings from 12-lead ECG, and clinical laboratory test results (biochemistry, hematology, and urinalysis).

Clinical laboratory tests, vital signs, and ECG findings will be summarized by treatment group and visit. Potentially clinically important findings will also be summarized or listed.

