7.1 Adverse Events

Adverse events will be coded using MedDRA Version 21.1.

An AE (classified by PT) will be considered a treatment-emergent AE (TEAE) if it starts on or after dosing on Day 1, or if it starts before dosing on Day 1 but increases in severity on or after dosing on Day 1 through the end of the study. If more than 1 AE with the same PT is reported before dosing on Day 1, then the AE with the greatest severity will be used as the benchmark for comparison to the AEs occurring after dosing on Day 1 under the PT.

Treatment most recently taken when the AE occurred will be used for the summaries:

- Any AE that started (or increased in severity) on or after the administration of anagrelide on Day 1, but before the administration of omeprazole on Day 2 will be assigned to anagrelide alone;
- Any AE that started (or increased in severity) on or after the administration of omeprazole on Day 2, but before the administration of anagrelide on Day 8 will be assigned to omeprazole alone;
- Any AE that started (or increased in severity) on or after the administration of anagrelide on Day 8 will be assigned to anagrelide with omeprazole.

An overall summary of the number of subjects with TEAEs as well as the number of events will be presented by treatment group, including the number and percentage of subjects with any TEAEs, serious TEAEs, TEAEs related to investigational product, serious TEAEs related to investigational product, TEAEs leading to discontinuation of investigational product, serious TEAEs leading to discontinuation of investigational product, TEAEs leading to discontinuation from study, serious TEAEs leading to discontinuation from study, severe TEAEs, TEAEs leading to hospitalization, and TEAEs leading to death.

The number and percentage of subjects reporting TEAEs, as well as the number of events, in each treatment group and overall will be tabulated by SOC and PT, and by SOC, PT, and maximum severity. The TEAEs considered related to investigational product will also be summarized by SOC and PT. If more than 1 AE occurs with the same PT, after the same treatment for the same subject, then the subject will be counted only once for that treatment group and PT using the most severe and most related occurrence for the summarization by severity and by relationship to investigational product. Summaries by SOC and PT will present SOC sorted alphabetically and PT within SOC by descending incidence.

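### Read literally, the adverse event rules count an episode that changes grade more than once, and count it again under the next treatment if it eases after the Day 2 or Day 8 dose

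*Protocol*

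**What the plan says.** **How events are recorded.** Protocol 8.1.1 requires severity to be recorded over the course of an event, "including the start and stop dates for each change in severity", and adds: "An event that changes in severity should be captured as a new event". Neither statement is limited to worsening. Worsening of events present before treatment has its own sentence.

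**What counts as treatment-emergent.** Under SAP 7.1 an adverse event is treatment-emergent if it starts at or after Day 1 dosing, or "if it starts before dosing on Day 1 but increases in severity on or after dosing on Day 1". The severity test applies only to events that began before dosing.

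**How events are assigned to a treatment.** SAP 7.1 states: "Treatment most recently taken when the AE occurred will be used for the summaries". Three windows follow. The middle one covers "Any AE that started (or increased in severity) on or after the administration of omeprazole on Day 2" and closes at the Day 8 anagrelide dose; those events go to omeprazole alone. The windows before and after it use the same bracketed wording.

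**What is reported.** SAP 7.1 plans both counts: "An overall summary of the number of subjects with TEAEs as well as the number of events will be presented by treatment group". Protocol 9.9 agrees: "The number of events, incidence, and percentage of treatment-emergent adverse events will be calculated overall", and also by system organ class, preferred term and treatment group. The secondary endpoint in the protocol synopsis includes the number of treatment-emergent events, assessed for anagrelide alone, omeprazole alone and the combination.

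**De-duplication.** The only rule, in SAP 7.1, counts a subject once per preferred term after the same treatment, using the most severe and most related occurrence.

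**The concern.** The two documents use different units. The protocol creates a record at each change of grade. The SAP counts and assigns adverse events without saying whether its unit is that record or the whole episode. If it is the record, an improving event produces a new start date, and a new start date is what the SAP uses to choose the treatment column.

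Two outputs are exposed. The number of events rises with every change of grade, whenever it happens. Subject incidence by treatment rises when the change falls after the next treatment has been given: a subject recovering from an anagrelide event can appear under omeprazole alone, and a subject recovering from an omeprazole-period event can appear under the combination.

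This matters because the secondary objective is safety and tolerability in each of the three treatment states. In a single-sequence study without a control group, the time windows are what separates those states. Causality would not reliably correct the column: Protocol 8.1.2 rates events as related or not related to the investigational product and describes no separate rating for anagrelide and omeprazole.

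**Working it through.** The documents state no figure on this point, so there is none to reproduce. The check applies the written rules to one assumed episode.

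**Inputs**
- Dosing at about 08:00 each day (Protocol 6.2.2). Taking Day 1 anagrelide as 0 h, the Day 2 omeprazole dose is at 24 h and the Day 8 dose at 7 × 24 = 168 h.
- Windows from SAP 7.1: 0 h to before 24 h is anagrelide alone; 24 h to before 168 h is omeprazole alone; from 168 h is the combination.
- About 20 subjects (Protocol 9.6), all assumed to reach the Day 2 dose.
- Assumed episode: a moderate headache starting at 2 h that eases to mild at 6, 23.5, 24 or 26 h.

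**Result under the literal rules.** Protocol 8.1.1 gives two records: moderate from 2 h, and mild from the time of easing. Both start after Day 1 dosing, so both are treatment-emergent.

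| Eases at | Anagrelide alone (events / subjects) | Omeprazole alone (events / subjects) | Total events |
|---|---|---|---|
| 6 h | 2 / 1 | 0 / 0 | 2 |
| 23.5 h | 2 / 1 | 0 / 0 | 2 |
| 24 h | 1 / 1 | 1 / 1 | 2 |
| 26 h | 1 / 1 | 1 / 1 | 2 |

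**Result with one record per episode.** For every easing time: anagrelide alone 1 / 1, omeprazole alone 0 / 0, total 1 event.

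**Reading the comparison**
- The event count is 2 instead of 1 in every row. An episode going mild, moderate, mild gives 3 records, so 3 events instead of 1.
- In the first two rows the de-duplication rule works: the subject counts once, at moderate. Only the event count is wrong.
- In the last two rows that rule does not apply, because it operates within one treatment. The subject is counted under both treatments.
- The anagrelide-alone column keeps its subject in every row. The omeprazole-alone count is an addition, not a transfer.
- Overall subject incidence is unchanged, since the subject already counts through the onset record.

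**Size in a table row.** Excess incidence = affected subjects not already counted in that row ÷ subjects in the column.
- 1/20 = 5.0 percentage points
- 2/20 = 10.0 percentage points
- 3/20 = 15.0 percentage points

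These are ceilings. A subject who already has another omeprazole-period event in the same row adds nothing. With an assumed denominator of 18 after dropouts, one subject is 1/18 = 5.6 points.

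**Safeguards looked for.** SAP 7.1 sets a severity benchmark for events of the same preferred term reported before Day 1 dosing, but has no equivalent at the Day 2 and Day 8 boundaries. No text links an eased record to the record that it continues. SAP section 13 lists no change from the protocol.

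**The case against.** The strongest reply is that the SAP's wording points the other way. If every severity-change record counted as a start, the bracketed words in "Any AE that started (or increased in severity) on or after the administration of omeprazole on Day 2" would do nothing, because the protocol already makes each worsening a new record. The words have a purpose only if a continuing event moves on worsening and stays put on easing. SAP 7.1 also classifies an adverse event by preferred term, which suggests a unit larger than the record. This stands as evidence of intent, and it makes the point an ambiguity rather than a rule that certainly yields a wrong table. It does not settle the matter: an eased record still has a start date in the later window, and nothing excludes it. Two competent programmers could produce different tables from the same data.

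Frequency is the second reply, and it stands. Protocol 1.2.1 describes events at 1 mg/day in healthy subjects as mainly mild, and a mild event has no lower grade to ease to. The Day 2 route needs a moderate or severe event that persists for roughly a day after one dose and then drops a grade. Such cases may be few.

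Third, table specifications sit in a separate shells document (SAP section 1), which may define how events are counted. That is possible, but it cannot be assumed to override a rule that the SAP itself states.

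A reader might infer that incidence is shifted from the causing treatment to the next, or that every easing event adds 5 points. The documents support neither. The onset record stays in its own window, and counting a subject once per treatment and preferred term makes 5 points a ceiling per subject and row.

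**Conclusion.** The point holds as an unresolved conflict between the recording rule and the counting rule. Taken literally, every change of grade inflates the number of treatment-emergent events. An episode that eases after the Day 2 or Day 8 dose also adds a duplicate count of that subject under the next treatment.

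The excess in subject incidence is at most 5 percentage points per affected subject in a row, assuming 20 subjects in the column, and zero where the subject already counts in that row. How many subjects would be affected cannot be derived from the documents; the two- and three-subject figures are illustrations only.

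For episodes that begin after Day 1 dosing, three things are unaffected: subject incidence when all records fall under one treatment, overall subject incidence, and the primary pharmacokinetic analysis. The consequence is confined to descriptive secondary safety tables. It still deserves correction, because event counts and by-treatment incidence are prespecified outputs and the remedy is cheap.

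**What to change.** Add to SAP 7.1:
- Contiguous severity-change records of the same preferred term in one subject, where one record stops as the next starts, form a single episode.
- The episode is counted once, at maximum severity, under the treatment at onset.
- It is counted under a later treatment only if severity increases there. In that case the SAP should say which severity each column carries, and whether the overall event count is one or two.
- A record that reflects easing opens no new treatment-emergent event and no new attribution.
- All records, with their dates and grades, stay in the listings.

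This follows the evident intent of the SAP's bracketed wording. It needs a few sentences and a short programming step before database lock, with no new data and no change to how the site records events. The downside is that two truly distinct but contiguous events of the same preferred term would be merged; the listings would still show them.
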